9.2.4 Data Acquisition and Entry

Data collection for this study will be accomplished with online electronic case report forms.

- On-line forms will be developed that contain the requisite data fields.
- For each subject enrolled all study-related visits of the enrollment, diagnostic, application, observation, termination and follow-up phases will be recorded in the CRF. This CRF must be completed and signed by the investigator for every subject on whose behalf written informed consent was given. This also applies to subjects who fail to complete the study. If a subject is being withdrawn from the study by his/her parent(s)/legal guardian(s), the reason must be stated in the CRF, if the parent(s)/legal guardian(s) are willing to provide such reason. If a subject is withdrawn from the study because of a limiting AE, reasonable efforts should be made to clearly document the outcome.
- All subjects will be identified by their subject number.
- Each investigator will be responsible for ensuring that the identification of his/her subjects is possible at any time.
- The investigator will use CRF Completion Guidelines to ensure that data is complete and accurate. These guidelines will provide instructions on how to complete, correct, and archive final copies of the CRFs.
- Prior to the beginning of the study, the investigator must establish a list of the individuals with trial related duties and of the persons authorized to make entries and data changes in the CRFs.
- These persons will be listed, including details on their function in the study, their full names, initials, and signatures, and the date of their assignment to (and, if applicable, their demission from) their respective duties on this study, on the center sample signature page in the investigator's file.

9.2.5 Data Editing

A number of data checks and procedures may be applied during data collection that either prevent errors or detect them with the requirement for later review and adjudication. No matter what the data source all data must pass through all predefined data checks and all potential errors must be reviewed and corrected or accepted with comment. Any discrepancies are reported in a data exception feedback report for correction and are monitored to ensure that they are accepted or corrected. Predefined procedures and data checks include:

- choosing forms and participants for data entry from the list of predefined enrollees avoiding the errors that can occur when ID numbers are entered directly on forms;
- implementing validation and consistency checks before data are sent to the database to allow correction but logging of all uncorrected exceptions for required later review; and

- checking for and recording on each form the rate of missing data that can be used to set criteria for subsequent forms processing, e.g. to reject forms with high missing data rates from entering the database; and
- flag out of range values
- creating a context sensitive comment window that allows subsequently retrievable text to be linked to any form or data item, e.g., to explain an unusual data response.
 Web-based, forms allow data to be viewed and edited. Quality assurance checks are applied during data entry and editing. In addition to maintaining a time-stamped audit trail of all logins and transactions, the system has the capability to be proactive, for example in requiring all unflagged data corrections be accompanied by a justification as well as to be adjudicated, reviewed, accepted or rejected, by a designee. Together these options and procedures promote a high degree of completeness, and accuracy of study data.

9.2.6 Data Entry Training

Data entry training will be conducted on line using the REDCap database and OnCore and Advarra databases. Study coordinators will be trained and certified in on-line use of the REDCap and OnCore databases. Training sessions will be scheduled and organized by members of the study team.

9.2.7 Data Quality Assessment (QA)

Data quality is assessed at the data entry point using intelligent review and controls during on-line data entry or edits via study forms. QA reports assess data quality postdata entry. Data quality begins with the design of the data collection forms and procedures and incorporates reasonable checks to minimize transcription and omission errors. Equally important quality assurance measures are the internal checks for reasonableness and consistency that will be implemented via simple tabulations and cross tabulations that should reveal any remaining data quality issues.

9.3 Confidentiality

By conducting this study, the investigator pledges that he/she will keep all information pertaining to the study strictly confidential, including data generated from this study, except as exempted for regulatory purposes.

Blood and urine samples will be collected and diagnostic records will be reviewed. Data recorded will include demographics, clinical summary, diagnostic tests and study results. All research data, including identifiers, will be accessible only to the research team and as required by law.

9.4 Regulatory and Ethical Considerations

9.4.1 Data and Safety Monitoring Plan

A DSMB has been assembled by the investigators. This Board is responsible for safety and accuracy monitoring of the data entered by the investigators. The DSMB will regularly evaluate trial performance, monitor interim data for safety and effectiveness of study regimens, review any protocol modifications, and advise the investigators regarding early termination or continuation of a study based on the interim monitoring or scientific findings. The DSMB will receive and respond to reports of any serious adverse events (SAEs) and will be immediately notified of fatal or life-threatening events. Based on the review of safety, efficacy, and performance data, the DSMB will make recommendations regarding conduct of the study. It is expected that the DSMB will meet as per the DSMB Charter.

9.4.2 Risk Assessment

9.4.2.1 Risks associated with Baricitinib

Baricitinib is Janus Kinase inhibitor which blocks the intracellular signaling response of interferon by limiting downstream activation of the interferon receptor. Janus Kinase inhibitors, including baricitinib, may therefore have risks associated with infection, as well as other serious risks. These are detailed below, and further information is available in prescribing information.

9.4.2.1.1 Serious Infections and Viral Reactivation

Serious and sometimes fatal infections due to bacterial, mycobacterial, invasive fungal, viral, or other opportunistic pathogens have been reported in rheumatoid arthritis patients receiving baricitinib. The most common serious infections reported with baricitinib included pneumonia, herpes zoster, and urinary tract infection (see Adverse Reactions).

Among opportunistic infections, tuberculosis, multidermatomal herpes zoster, esophageal candidiasis, pneumocystosis, acute histoplasmosis, cryptococcosis, cytomegalovirus, and BK virus were reported with baricitinib. Some patients have presented with disseminated rather than localized disease and were often taking concomitant immunosuppressants such as methotrexate or corticosteroids.

As of March 2020, fungal pneumonia was reported in a single AGS patient receiving baricitinib and also receiving concomitant therapy with corticosteroids during the Lilly expanded access program. Vigilance for infections should remain high in particular in children with any concomitant medications increasing immunosuppression, or hematologic parameters suggestive of immunosuppression.

Prophylaxis for serious infections will be recommended based on CD4, IgG, ANC and ALC levels as per section 4.6.

To minimize these risks, screening includes careful assessment of infections prior to drug initiation, including HIV, hepatitis, tuberculosis, HSV, CMV, EBV, and BK virus. In addition, ongoing evaluations, including clinical assessments for infection, and laboratory testing for HSV (IgG/IgM), CMV PCR, EBV PCR and tuberculosis (via quantiferon gold testing, only for patient in endemic regions) during treatment, will be conducted as clinically indicated.

Patients will be monitored for BK viremia at baseline, and every six months until they reach two years of age. Over two years of age, complete follow-up BK testing will be performed if any of the following is observed: blood in urine not explained by a urinary

tract infection (as defined by greater than 10 RBCS in HPF), equal to or greater than 1+ protein on a first morning urine sample not explained by a urinary tract infection (positive), decrease in eGFR ($30 - 60 \text{ mL/min}/1.73 \text{ m}^2$).

Children with AGS are at risk of respiratory, skin and urinary tract infections as part of their disease. Unless these infections fall into the categories below, there will not be drug discontinuation for these events. Patients will receive treatment as clinically indicated for these infections. Discontinuation of baricitinib has been associated with neurologic decline in patients with AGS¹⁷, leading to greater caution around holidays from drug therapy in the context of acute infections.

Certain categories of infections will require specific management:

Serious infections are defined as those resulting in or occurring during hospitalization, or need for parenteral antimicrobial treatment. In these cases, the diagnostics and treatment plan will be discussed with local infectious disease team for decisions regarding continuation, decrease or interruption of study treatment. All events where infection is associated with hospitalization or need for parenteral antimicrobial treatment will be reported to the DSMB and IRB as a SAE within 24 hours of learning of the event. Patients will receive treatment as clinically indicated regardless of treatment decisions for baricitinib.

Disseminated/complicated herpes zoster, for which drug cessation will occur until improvement in symptomatic herpes zoster infection occurs (resolution of PCR positive serologies or all lesions crusted) as confirmed by local infectious disease team. Disseminated/complicated herpes zoster is defined as multidermatomal involvement in cases of reactivation, central nervous system involvement or systemic involvement including hepatitis or pneumonitis). After improvement, baricitinib may be resumed. Herpes zoster that is not confirmed, is self resolving, limited to skin without CNS, hepatic or pulmonary involvement, will result in discussion with local infectious disease team but will not result in immediate drug discontinuation. The infection will be managed as clinically indicated. Patients will receive treatment as clinically indicated regardless of treatment decisions for baricitinib. All events of disseminated/complicated herpes zoster will be reported to the DSMB and IRB within 24 hours of learning of the event as a reportable event.

Viral reactivation, including EBV/CMV reactivation. In these cases, the diagnostics and treatment plan will be discussed with local infectious disease team for decisions regarding continuation, decrease or interruption of study treatment. Viral reactivation, including cases of herpes virus reactivation (e.g., herpes zoster), were reported in clinical studies with baricitinib. If a patient develops disseminated/complicated herpes zoster, we will interrupt treatment until the episode resolves (i.e. until symptomatic improvement of the herpes zoster occurs). EBV and CMV may also be reactivated during treatment, and both EBV and CMV will be monitored during study safety laboratory testing (via PCR) if hematologic or hepatologic parameters suggest infection. If a patient develops clinically relevant reactivation, we will notify local infectious disease team to establish whether to continue, decrease or interrupt treatment until improvement is seen in viral titers or organ involvement (see Appendix 15). All events of EBV/CMV reactivation will be reported to the DSMB and IRB

within 7 days of learning of the event as a reportable event. Patients will receive treatment as clinically indicated regardless of treatment decisions for baricitinib.

Infections occurring in cases where ANC, ALC, IgG, CD4 are at levels that need additional monitoring as defined in the protocol. In these cases, the diagnostics and treatment plan will be discussed with local infectious disease team for decisions regarding continuation, decrease or interruption of study treatment. All events will be reported to the DSMB and IRB within 7 days of learning of the event as a reportable event. Patients will receive treatment as clinically indicated for these infections regardless of treatment decisions for baricitinib.

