4.4.2 Initial Treatment and Dose Escalation

Baricitinib will be dosed by patient age, weight range and eGFR. See Appendix 3 for the dosing schedule for patients with eGFR \geq 60 mL/min/1.73 m² or normal eGFR for patients age <24 months (eGFR \geq 60 mL/min/1.73 m²). eGFR will be calculated using the *Bedside Schwartz Equation:* eGFR (mL/min/1.73 m²) = (0.413 x height) / S_{Cr}, with height measured in cm, and serum creatinine (S_{Cr}) in units of mg/dL. The creatinine should be measured using the IDMS (Isotopic Dilution Mass Spectrometry) technique to monitor the eGFR if available. Other methods are allowed but are not preferred. Laboratory testing using other methods will not be used to monitor the eGFR. Tolerance will be judged by stability or improvement in hematology and chemistry laboratory test results collected as specified in Study Schedule (Appendices 1 and 2). See Appendix 4 for the dosing schedule for patients with eGFR 30 - <60 mL/min/1.73 m²).

Patients must receive a dose for at least 72 hours before a dose escalation can occur. Safety laboratory data will be assessed according to the Study Schedule (Appendices 1 and 2).

Every effort should be made to follow the dose escalation schedule shown in Appendices 3 and 4. However, if a patient's condition warrants an accelerated dose escalation schedule, dose reduction, interruption, or discontinuation, this may be allowed after review of the patient's clinical data and consultation with the subinvestigators. Additionally, in the event of AEs possibly attributable to the study drug, the dose may need to be reduced. These decisions should be taken following documented consultation, and agreement between the investigator and subinvestigators, and approval from the IRB prior to initiating the dose modification. Only in emergency situations will the investigator take subsequent dose restarts or increments after review of clinical data, documented agreement between the investigator and subinvestigators, and notification of the IRB.

Attention will be given to concomitant medications, in particular those that are exclusion criteria (Appendix 16).

Where needed, clinical pharmacists will be contacted about the need for dose adjustment and for guidance related to concomitant therapies that must be used with caution.

In the event that it is necessary to contact a clinical pharmacist, the study team can page the 24/7 on-call clinical pharmacist.

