4.8 Dosing changes

On occasion, if drug related adverse events are seen, changes or discontinuation of study medication will be considered. Because abrupt drug discontinuation may result in rebound inflammation, tapering of dosing to the next dosing increment (e.g. 2 mg three times a day to 2 mg twice a day – Appendix 14) may be considered in response to suspected drug related adverse events. Repeat laboratory testing will be performed after drug tapering and results will be discussed with the study team to assess that drug continuation at a lowered dose is in the best interest of the patient.

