4.9 Subject Completion/Withdrawal

On occasion, the investigator may find it necessary to decrease (Appendix 14), temporarily interrupt or prematurely permanently discontinue investigational product administration following the occurrence of an AE or an abnormal laboratory finding. The investigator must notify the DSMB within 48 hours when decreasing, temporarily interrupting or prematurely permanently discontinuing therapy for an individual. If infection is the cause of the interruption, patients will receive treatment as clinically indicated for infections regardless of treatment decisions for baricitinib.

Any patient who is permanently discontinued from investigational product for an abnormal laboratory result should have the abnormal laboratory result reported as an AE, or an SAE if the laboratory abnormality results in an outcome requiring the AE to be reported as an SAE.

In addition, patients may be discontinued from the investigational product or from the study in the following circumstances:

- The patient enrolls in any other clinical trial involving an investigational product or in any other type of medical research judged not to be scientifically or medically compatible with this study.
- An SAE or a clinically significant change in a laboratory value occurs that, in the opinion of the investigator, merits the investigational product being discontinued and appropriate measures being taken.
- The investigator decides that the patient should be withdrawn from the study.
- The parents, legal guardian, or patient requests to be withdrawn from the study.
- Investigational product is no longer supplied.

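### Section 4.4.2 asks for IRB approval before safety-driven dose changes that Sections 4.8, 4.9 and 5.2.13 allow without it; separately, the zoster restart test names no organ criterion

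*Combined protocol and SAP*

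**What the plan says.** **Dose changes, Section 4.4.2.** After urging adherence to the escalation schedule, the section says that if a patient's "condition warrants an accelerated dose escalation schedule, dose reduction, interruption, or discontinuation, this may be allowed after review" of the clinical data and consultation with the subinvestigators. It then adds that "in the event of AEs possibly attributable to the study drug, the dose may need to be reduced. These decisions should be taken" after documented consultation, "agreement between the investigator and subinvestigators, and approval from the IRB prior to initiating the dose modification". The emergency provision reads: "Only in emergency situations will the investigator take subsequent dose restarts or increments after review of clinical data", with documented agreement and notice to the IRB.

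**Dose changes elsewhere.** Section 4.8 says that tapering to the next dose step "may be considered in response to suspected drug related adverse events". Section 4.9 allows a decrease, interruption or permanent stop after an adverse event or abnormal laboratory result, and adds: "The investigator must notify the DSMB within 48 hours when decreasing, temporarily interrupting or prematurely permanently discontinuing therapy for an individual". It expects infection to be one reason: "If infection is the cause of the interruption, patients will receive treatment as clinically indicated for infections regardless of treatment decisions for baricitinib". Section 5.2.13 has interruption weighed with the study team and the treating clinicians under Appendices 9 to 12. Appendices 10 to 12 set laboratory triggers for reducing or stopping the drug and leave the discontinuation decision with the investigative team. None of these texts mentions prior IRB approval.

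**Zoster, Section 9.4.2.1.1.** Disseminated or complicated zoster is a condition "for which drug cessation will occur until improvement in symptomatic herpes zoster infection occurs (resolution of PCR positive serologies or all lesions crusted"). The sentence goes on to require confirmation by the local infectious disease team, and the drug may then be restarted. The class is defined to include CNS disease, hepatitis and pneumonitis. The event is reported to the DSMB and IRB within 24 hours. The viral reactivation paragraph of the same section restates the hold as lasting until the episode resolves, which it explains as symptomatic improvement.

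**The concern.** An investigator facing an adverse event needs one rule for whether the dose can be changed today. Section 4.4.2 asks for the IRB's approval first and sets no time limit for it. Section 4.9 says to act and then tell the DSMB. Staff who follow 4.4.2 literally could delay a reduction of an immunosuppressant, or record as a deviation a change that another section provides for.

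Restart after complicated zoster raises a separate question. The written test is about PCR results or skin lesions, while the condition it covers includes disease of the brain, liver and lung. Crusting can meet the written test while organ disease is still active, which leaves protection to the local team's judgement. What is at stake is participant safety and clean conduct, not any estimate or test in Section 6.

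**Working it through.** The plan states no figure on this point and no arithmetic applies. The check is a comparison of the texts.

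**Step 1: what 4.4.2 covers.** The sentence on IRB approval opens by referring to these decisions. The nearest antecedent is the sentence on dose reduction for adverse events possibly due to the drug, so that case is plainly included. The sentence before it lists reduction, interruption and discontinuation, and the natural reading takes those in too. The verb is *should* rather than *must*, but no condition is given under which the step may be skipped.

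**Step 2: the exception.** The emergency sentence names restarts and increments. It does not name reductions, interruptions or stops, so the changes most likely to be urgent for safety are outside it. It is also unclear whether it confines restarts to emergencies or only lets emergency restarts go ahead on notice. Either way it asks for more than 9.4.2.1.1 does for a zoster restart.

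**Step 3: the same action under each rule.**
- *Reduction for a suspected drug-related event.* 4.4.2: IRB approval first. 4.8: may be considered, with repeat laboratory tests discussed with the study team. 4.9: may be done, with DSMB notice within 48 hours. The conflict is direct.
- *Interruption or stop for an adverse event or laboratory value.* 4.4.2, on its natural reading: IRB approval first. 4.9: DSMB notice within 48 hours. 5.2.13 and Appendices 10 to 12: decided by the study team. The conflict is real but depends on how far 4.4.2 reaches.
- *Stop for disseminated or complicated zoster.* 9.4.2.1.1 orders it, with a report of the event within 24 hours. 4.4.2 neither orders nor exempts it, so what is missing is an exemption.

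**Step 4: precedence.** No sentence in the readable text says which section governs when they differ. Nor is 4.4.2 confined to first dosing: Sections 4.5.1 and 4.5.2 send later dose escalation back to the earlier dosing text.

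**Step 5: the restart test.** The two limbs, PCR resolution and crusting of all lesions, are joined by *or*, so crusting alone can satisfy the parenthesis. What the infectious disease team confirms is improvement as the parenthesis defines it, so confirmation adds a clinician but no organ criterion. By contrast, the EBV/CMV rule in the same section looks to improvement in viral titers or in the affected organ. An organ-based criterion was therefore available to the authors and is absent for zoster.

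**The case against.** The best defence is that 4.4.2 concerns initial dosing and elective departures from the escalation schedule. On that view a stop that the protocol orders leaves nothing to approve, because the IRB has already approved the protocol (Section 8). Sections 4.9 and 5.2.13 and the authority retained in Appendices 10 to 12 are the natural rules for safety changes, and Section 9.8.8 gives a route for emergencies. Much of this stands. It does not dispose of reductions for adverse events, which 4.4.2 itself brings under the approval sentence, and the 9.8.8 route treats prompt action as a protocol deviation.

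A reader might infer that the protocol makes a zoster stop wait for the IRB. The documents do not support that: 9.4.2.1.1 says cessation will occur, and 4.9 fits the case better than 4.4.2. Nor do the 24-hour and 48-hour requirements contradict each other. One concerns the event, the other the dose change, and both can be met. The laboratory stopping rules in Appendices 10 to 12 do not add urgency either: they appear under criteria for consideration, and most work through stepwise tapers.

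On restart, a reader might infer that crusted skin alone puts a child with CNS zoster back on drug. That is too strong. The local team must confirm improvement, restart is permitted rather than required, and the second statement of the rule refers to the episode resolving. The two limbs could also be read by site, with PCR for systemic disease and crusting for skin. Zoster that leads to hospitalization or parenteral treatment also falls under the serious-infection paragraph, which brings in the infectious disease team and a 24-hour SAE report. Appendix 15, the infection decision tree, is a figure not shown in the text available here and may settle restart.

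**Conclusion.** The main point holds as an unresolved conflict between sections. Section 4.4.2 asks for IRB approval before dose changes that 4.8, 4.9, 5.2.13 and Appendices 10 to 12 allow without it, and its emergency sentence does not cover reductions or stops. The conflict is firmest for reductions driven by adverse events, weaker for interruptions and discontinuations in general, and only a missing exemption for the ordered zoster stop.

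The restart point holds in smaller form: the written test names no recovery criterion for CNS, hepatic or pulmonary disease, although specialist confirmation and optional restart limit the risk.

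The size cannot be put in patients. The documents give no rate of disseminated zoster in this population, and none is assumed. No endpoint, analysis or power figure changes. The conclusion assumes that the sections are read as written and that Appendix 15 contains no overriding rule, which could not be checked. The change is worth making because a rule followed literally could delay a safety action and the correction costs little. Confidence is medium.

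**What to change.** **Section 4.4.2.** Add after the IRB-approval sentence: *Dose reductions, interruptions or discontinuations for safety under 4.8, 4.9, 9.4.2.1.1 or Appendices 9 to 12, 14 and 15 take effect at once without prior IRB approval. The DSMB and IRB are notified as those sections state, and restart follows the criterion in the section that ordered the stop.* Departures not provided for elsewhere would still need IRB approval.

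**Section 9.4.2.1.1, zoster paragraph.** Keep both limbs of the restart test and the infectious disease team's confirmation. Add a condition that applies whichever limb is met: *and, where there is CNS, hepatic or pulmonary involvement, improvement of that involvement.* Improvement is a better standard than full resolution here, because encephalopathy and hepatitis are features of AGS itself (Section 8.4.1), and Appendix 9 puts baseline hepatic involvement at one-third of patients.

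**Viral reactivation paragraph and Appendix 15.** Point the second statement of the zoster hold to the same test, and check that the decision tree agrees.

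The cost is one text amendment, with no added patients, visits or scheduled tests. The downside is a possibly longer hold in the few cases with organ involvement, to be weighed against the neurologic decline that 9.4.2.1.1 associates with stopping baricitinib.
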